3. INVESTIGATIONAL PLAN

3.1 Study Design

This is a randomized, controlled, third-party blind, single-center study in healthy volunteers where each subject receives 2 of the 3 possible study products on the groin. The study staff performing the bacterial enumeration and the statistician performing the analysis will be blinded to the study products.

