3.2 Randomization

The left and right test areas on the subject's inguinal region will be assigned according to a computer-generated randomization schedule where each will receive 1 of the 3 study products (see Table 1). Treatment randomization will be balanced between left and right sides. There are 3 different possible combinations of treatments. These are shown below in Table 2.

To provide enough subjects to meet study objectives, the treatment combinations will be randomized in a 6:1:1 ratio for combinations 1 through 3, respectively, at the single recruiting clinical facility. The details of block size will be documented in the final study report.

Baseline and post-prep samplings at 10 minutes and 6 hours will be randomized to three sites within each test area. The same test site randomization will be used on the left and right sides of a subject's body to reduce the possibility of sampling errors.

The Investigator is responsible for ensuring that the study randomization is followed. Randomization envelopes will be provided to the study site.

CDT

Table 1 Study Products

Treatment Code	Study Product	Description
SP	SoluPrep	Contains 2% w/v chlorhexidine gluconate (CHG) and 70% v/v isopropyl alcohol (IPA). 10.5-mL applicator, tinted.
SPFF	SoluPrep FF	Contains 2% w/v chlorhexidine gluconate (CHG) and 70% v/v isopropyl alcohol (IPA) in combination with an acrylate copolymer. 10.5-mL applicator, tinted.
S	Saline	Negative control. Sterile 0.9% saline. 20-mL bottle.

Table 2 Subject Treatments

Treatment Combination	Left and Right Treatment
1	SoluPrep 10.5-mL and SoluPrep FF 10.5-mL (SP + SPFF)
2	SoluPrep 10.5-mL and saline (SP + S)
3	SoluPrep FF 10.5-mL and saline (SPFF + S)

Randomization Plan:

A 3M statistician not assigned to the project will develop a randomization program and generate the randomization code list. The code list will include randomization number, left side treatment, right side treatment, baseline sample site, 10-minute sample site and 6-hour sample site. The randomization assignments will be printed and inserted into security envelopes then tightly sealed.

The Data Manager will strip the treatment assignment from the programs that are used to download the data from Clindex®. This will keep the statistician assigned to the study blinded until data lock.

CDT

Randomization Process:

For each eligible subject to be randomized, the investigator or designee will do the following:

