5.2 Modified Intent-To-Treat Population (MITT)

A MITT data set will be used for primary efficacy analyses. All subjects who meet baseline requirements on a bilateral side will be included in the analysis for that bilateral side. However, the primary analyses involve a linear regression at the 10-minute post-treatment time point and calculation of return to baseline at 6 hours. These analyses require both baseline and 10-minute recovery for treatment effect or baseline and 6-hour recovery data for return to baseline percentage calculation. There is no scientific basis for imputation of these missing values. Fortunately, missing values are not expected. There was no missing data for the 2346 microbiological samples taken in the pivotal study conducted at this site for SoluPrep FF. The exclusion of subjects who do not meet baseline requirements and who are missing recovery data at either the 10-minute sampling time point or the 6-hour sampling time point (post-treatment) times makes this data set a modified intent-to-treat data set.

The baseline bacterial count requirements are in the range of 5.00 to 7.50 \log_{10}/cm^2 on the groin. The acceptability of each bilateral baseline will be assessed separately for inclusion in the study.

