6.2 Determination of Sample Size

The Final Monograph (21 CFR Part 310 Safety and Effectiveness of Health Care Antiseptics; Topical Antimicrobial Drug Products for Over-the-Counter Human Use) calls for a minimum of 100 observations per treatment. A standard deviation of 1.0 \log_{10}/cm^2 was observed in study EM-05-012760. One-hundred subjects per treatment arm

CDT

provides 94% power using a non-inferiority margin of $0.5 \log_{10}/\text{cm}^2$ with a 1-sided alpha of 0.025.

In the same study, a superiority to the negative control was observed to be approximately $2.5 \log_{10}/\text{cm}^2$, with a lower 95% confidence bound of $2.26 \log_{10}/\text{cm}^2$. A sample size of 30 for the negative control will ensure that the mean for \log_{10}/cm^2 reduction of skin flora relative to Treatment Day baseline will be normally distributed. With 100 observations for the active products and 30 observations for the negative control, the mean observed difference must be greater than $1.62 \log_{10}/\text{cm}^2$ for the lower 95% confidence bound to be greater than $1.2 \log_{10}/\text{cm}^2$. At these sample sizes and the lower 95% confidence bound of $2.26 \log_{10}/\text{cm}^2$, there is 79% power to show superiority to the negative control with a 1-sided alpha of 0.025.

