8. EFFICACY ANALYSIS

8.1 Primary Efficacy Analysis

The average treatment effect (ATE) for the investigational product will be estimated using a linear regression of the 10-minute post-treatment bacterial count (\log_{10} scale) on the additive effect of a treatment indicator and the baseline measurement (\log_{10} scale). The lower bound of the 95% confidence interval for the additive treatment effect must not include the investigational product being more than $0.5 \log_{10}/\text{cm}^2$ lower than the positive control.

The ATE of the test product compared to the negative control is estimated as the contrast of treatment effect of negative control minus the treatment effect of the test drug in the linear regression. Likewise, the ATE of the active control compared to the test product is estimated as the contrast of treatment effect of test product minus the treatment effect of the active control in the linear regression. Superiority to negative control uses a margin of $1.2 \log_{10}/\text{cm}^2$, which would be demonstrated by a lower bound of the 95% confidence interval for the contrast to exceed $1.2 \log_{10}/\text{cm}^2$.

An example code for the analyses specified above is shown below:

Proc Mixed data=D_14624.LogMicro;

Class Treatment;

CDT

```
Where Timepoint=1 and Treatment in (1 2);  
Model LogRecovery=Treatment LogBaseline/ddfm=kr;  
Lsmeans Treatment/cl;  
Run;
```

The percent of samples for which the 6-hours post treatment recovery is lower than the baseline recovery will be calculated by active product. Thus, if \log_{10} reduction is >0 the sample has not returned to baseline. The Final Monograph requires that these percentages be 100.

An example code for percentage return to baseline is shown below:

Proc Format;

```
value Return      -5-0='Returned to Baseline'  
                 0.0001-8='Did not Return to Baseline';  
run;
```

Proc Freq data=D_14624.LogMicro;

```
Where Timepoint=2;  
Tables LogReduction*Treatment/nopercent norow;  
format LogReduction return.;
```

Run;

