### **1.5 Study Population**

Healthy male and female volunteers, 18 years of age or older, with no dermatological conditions on the test sites, or known history of sensitivity to acrylates, CHG- or alcohol-containing products, medical tapes, metals, natural rubber latex, vinyl, or skin-marking inks, will be enrolled into this study. A sufficient number of subjects will be enrolled in the screening phase, such that approximately 100 applications of the investigational product (10.5-mL tinted) and the active control (10.5-mL tinted), in addition to approximately 30 applications of the negative control, are evaluable for efficacy on the inguinal region (groin) at completion of the study. In total, 230 evaluable applications of investigational product, active control, and negative control would require 115 test subjects, utilizing both the right and left sides of the inguinal region. With the expectation that 15% of subjects will not meet treatment day baseline requirements, it is anticipated that 135 subjects will need to be treated. Subjects must satisfy all Screening Day and

3M Confidential

Document Name: CLIN-PROT-ICH-US-05-658998

Clinical and Non-Clinical: CLIN-INDEX-3M-SPON-US-05-014624

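### The primary 10-minute model has no subject term, although about 85 of every 100 SoluPrep sides share a person with a SoluPrep FF side, so the non-inferiority interval has the wrong width unless the left/right residual correlation is zero

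*SAP*

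**What the plan says.** SAP 3.1 states that "each subject receives 2 of the 3 possible study products on the groin". Under SAP 3.2, "the treatment combinations will be randomized in a 6:1:1 ratio for combinations 1 through 3"; combination 1 is SoluPrep with SoluPrep FF, and combinations 2 and 3 pair one active product with saline. The sampling positions are also matched within a person: "The same test site randomization will be used on the left and right sides". Protocol 1.5 counts 230 evaluable applications, which "would require 115 test subjects, utilizing both the right and left sides of the inguinal region". Sides qualify one at a time (SAP 5.2): "The acceptability of each bilateral baseline will be assessed separately for inclusion in the study".

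For the primary analysis, the prose of SAP 8.1 and protocol 8.2.1 describes a linear regression of 10-minute recovery on treatment and baseline. The example Proc Mixed code selects rows with "Where Timepoint=1 and Treatment in (1 2", lists only Treatment in CLASS, and fits "Model LogRecovery=Treatment LogBaseline/ddfm=kr". It has no RANDOM or REPEATED statement. Neither document mentions a subject effect, pairing or left/right correlation.

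**The concern.** Most of the SoluPrep versus SoluPrep FF comparison is made within people, but the model treats every side as a separate person. The Kenward-Roger option does not repair this. With no random or repeated effect in the model, the fit is ordinary least squares with independent residuals.

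The non-inferiority decision rests on the width of this interval. If the two sides of a person remain positively correlated after baseline adjustment, the planned standard error is too large and precision is thrown away. If they are negatively correlated, it is too small and the false non-inferiority rate exceeds 2.5%. A positive correlation is the likelier case: both sides belong to one person, are prepped and sampled on the same day, and use the same sampling positions.

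**Working it through.** **Inputs.** From the documents: 100, 100 and 30 evaluable sides (SAP 3.2); 115 subjects (protocol 1.5); SD 1.0, margin 0.5 and one-sided alpha 0.025 (SAP 6.2, protocol 8.1). Assumed: rho, and that 1.0 is the residual SD. The documents do not say whether 1.0 refers to recovery, reduction or a baseline-adjusted residual.

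**The plan's own figure.** Two independent arms of 100, SD 1.0, margin 0.5, one-sided 0.025, noncentral t: power 94.0%. The stated 94% reproduces, and it reproduces under independence.

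**Number of pairs.** Let a, b and c be the subjects in combinations 1, 2 and 3. Then a + b = 100, a + c = 100 and b + c = 30, so a = 85 and b = c = 15. The ratio agrees: 115 × 6/8 = 86.

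**Standard errors for SoluPrep minus SoluPrep FF**, two-product fit as in the code, SD 1.0:

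- Reported by the planned model: √(2/100) = 0.141; half-width 1.972 × 0.141 = 0.279, whatever rho is.
- Actual SE of the planned estimate: √(0.02 − 2 × rho × 85/10,000).
- With a subject covariance: √(2/n*), where n* = 85/(1 − rho) + 15 is the equivalent number of independent sides per arm. The half-width uses t = 1.981 (113 df, assumed).

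Non-inferiority is shown if the upper bound of the difference in recovery is below 0.5. The planned one-sided error is Φ(−0.279/actual SE). Planned power at zero true difference is Φ((0.5 − 0.279)/actual SE). Power with the subject term uses the noncentral t.

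| rho | actual SE | n* | half-width, planned | half-width, subject term | planned one-sided error | power, planned | power, subject term |
|---|---|---|---|---|---|---|---|
| 0.1 | 0.135 | 109 | 0.279 | 0.268 | 2.0% | 94.9% | 95.6% |
| 0.2 | 0.129 | 121 | 0.279 | 0.254 | 1.5% | 95.7% | 97.1% |
| 0.3 | 0.122 | 136 | 0.279 | 0.240 | 1.1% | 96.5% | 98.4% |
| 0.5 | 0.107 | 185 | 0.279 | 0.206 | 0.5% | 98.0% | 99.8% |

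At rho −0.2 the actual SE is 0.153 and the planned error is about 3.4%.

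**Sensitivity to SD** (rho 0.2, 0.3, 0.5). Half-widths scale with the SD.

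- SD 0.8: 0.22 planned, against 0.20, 0.19 and 0.16. Power exceeds 99% under both models.
- SD 1.2: 0.33 planned, against 0.31, 0.29 and 0.25. Power is 86%, 87% and 90% planned, against 90%, 93% and 98%.

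**Broken pairs.** If 15% of the 85 pairs lose one side (85 × 0.85 = 72) and each product keeps 100 sides, n* = 72/(1 − rho) + 28. Half-widths at SD 1.0 are 0.258, 0.245 and 0.214.

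**Saline contrast** (15 pairs, plus 85 and 15 single sides). The planned SE is √(1/100 + 1/30) = 0.208. With a subject term it is 0.202, 0.197 and 0.183. Both are small against 2.26 − 1.2 = 1.06.

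**Does estimating rho cost anything?** In simulation with a baseline covariate and rho estimated by REML in each trial, the compound-symmetry model held its one-sided error at 2.3% to 2.6% for rho from −0.2 to 0.5. At rho 0 its mean half-width was 0.280 against 0.279, and its power 93.5% against 93.6%.

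**The case against.** The strongest reply is that little turns on this. With positive rho the planned test is conservative, a non-inferiority claim remains valid, and the 94% power is met. The gain at SD 1.0 is one to two percentage points, and the saline contrast barely moves. All of that is true. It limits the seriousness of the point, but it does not make the reported interval a 95% interval.

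Four narrower objections have some force.

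- **Small rho.** Adjusting for each side's own baseline removes part of the shared person effect, so rho could be small. At 0.1 the half-width falls only from 0.279 to 0.268. An unknown rho is still a reason to estimate it, not to fix it at zero.
- **SD 1.2.** This is a sensitivity case only. If the documents' 1.0 is the SD of recovery or of reduction, the adjusted residual SD would be no larger, unless this study is noisier than the earlier one.
- **Purpose of the two sides.** The documents use both sides to reach the number of applications. They do not claim a precision gain from pairing. The gain is available all the same.
- **The 85/15/15 split.** Strict 6:1:1 allocation with 30 saline sides would give 90/15/15. The planned half-width is then 0.272, against 0.248, 0.234 and 0.201, so the picture is unchanged.

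That the code is labelled an example does not help, because the prose in both documents specifies the same two-term model.

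**Conclusion.** The concern holds. The model omits a dependence that the design creates, and the primary interval is correct only at rho = 0. For rho between 0.2 and 0.5 the planned half-width of 0.28 should be 0.25 to 0.21, which is the precision of about 121 to 185 independent sides per arm instead of 100. The probable direction is conservative, so this is a loss of precision and a mis-stated confidence level, not a threat to a positive non-inferiority finding. Inflated error arises only if rho is negative, which is a sensitivity remark. The size depends on the assumed rho and residual SD, neither of which the documents settle. The omission and the pair count depend on neither. The plan should be changed, chiefly because the correction is almost free.

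**What to change.** Before unblinding, which SAP 1 allows for:

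1. Add Subject to CLASS and `Repeated / subject=Subject type=CS` to the Proc Mixed model. State the structure explicitly, because the default is diagonal and would again assume independence.
2. Say the same in the prose of SAP 8.1. Keep subjects who have only one evaluable side.
3. Take the SoluPrep minus SoluPrep FF difference and its 95% CI from an ESTIMATE statement or `Lsmeans Treatment/diff cl`, and report the estimated rho.
4. Use the same subject term for the saline contrasts.

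The two-product row selection can stay for non-inferiority. If all three products go into one model, as the contrasts in the prose suggest, state that it assumes a common residual variance, baseline slope and left/right correlation, or let the variance differ by product (for example `Repeated Treatment / subject=Subject type=CSH`). Pooling adds little to the non-inferiority comparison: half-width 0.20 against 0.21 at rho 0.5, and no visible gain at rho 0.2.

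The cost is one CLASS entry, one line of code, a sentence of text and one extra covariance parameter. Subject and side are already recorded.

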## 8.2 Statistical Methods

### 8.2.1 Efficacy Analyses

#### Primary Efficacy Analyses:

The average treatment effect (ATE) for the investigational product will be estimated using a linear regression of the 10-minute post-treatment bacterial count ( $\log_{10}$  scale) on the additive effect of a treatment indicator and the baseline measurement ( $\log_{10}$  scale). The lower bound of the 95% confidence interval for the additive treatment effect must not include the investigational product being more than  $0.5 \log_{10}/\text{cm}^2$  lower than the positive control.

The ATE of the test product compared to the negative control is estimated as the contrast of treatment effect of negative control minus the treatment effect of the test drug in the linear regression. Likewise, the ATE of the active control compared to the test product is estimated as the contrast of treatment effect of test product minus the treatment effect of the active control in the linear regression. Superiority to negative control uses a margin of  $1.2 \log_{10}/\text{cm}^2$ , which would be demonstrated by a lower bound of the 95% confidence interval for the contrast to exceed  $1.2 \log_{10}/\text{cm}^2$ .

The percent of samples for which the 6-hours post treatment recovery is lower than the baseline recovery will be calculated by active product. The Final Monograph requires that these percentages be 100.

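### The saline comparisons pool one residual variance across about 30 saline and 100 sides per active product, with no saline SD to support it, so their confidence intervals may have the wrong width

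*SAP*

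**What the plan says.** SAP 8.1 has the treatment effect "estimated using a linear regression of the 10-minute post-treatment bacterial count" on treatment and baseline. The saline comparison is "estimated as the contrast of treatment effect of negative control minus the treatment effect of the test drug in the linear regression"; protocol 8.2.1 says the same. Success requires the lower 95% bound of that contrast to exceed 1.2 log10/cm².

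The example PROC MIXED program has the model line "Model LogRecovery=Treatment LogBaseline/ddfm=kr". It has no REPEATED or GROUP= statement, so it estimates a single residual variance; the Kenward-Roger option does not alter that. The program is restricted by "Where Timepoint=1 and Treatment in (1 2", so it fits two treatments, and the numeric codes are not defined. Neither document says whether the saline contrasts come from one three-arm fit or from pairwise fits. No unequal-variance sensitivity analysis is planned.

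On arm sizes, SAP 3.2 states that "the treatment combinations will be randomized in a 6:1:1 ratio for combinations 1 through 3, respectively", which gives sides in the ratio 7:7:2. SAP 6.2 works out its superiority threshold "With 100 observations for the active products and 30 observations for the negative control". The only SD in either document is 1.0 log10/cm²; none is given for saline.

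**The concern.** A pooled variance is a weighted average, and here the active sides dominate it. The saline mean contributes most of the uncertainty in the saline contrast, because 1/30 is much larger than 1/100, yet its variance is borrowed almost entirely from the actives. If saline sides vary less than active sides, the interval is too wide and the test conservative. If they vary more, the interval is too narrow and the one-sided error exceeds 2.5%.

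One of the two 10-minute decisions rests on this bound, and SAP section 4 asks for superiority of both active products. The equal-variance assumption therefore needs support or a method that does without it, and the documents supply neither.

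**Working it through.** **Inputs.** From SAP 6.2: 100, 100 and 30 sides, SD 1.0, one-sided alpha 0.025, non-inferiority margin 0.5, superiority margin 1.2, planning difference 2.26. Assumed here: active SD exactly 1.0, saline SD *s* varied, left and right sides independent.

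**The plan's own figures.**
- Non-inferiority power: 0.5/√(2/100) − 1.96 = 1.576, so 94.2%. This reproduces the stated 94%.
- Superiority threshold: the standard error is √(1/100 + 1/30) = 0.2082. The observed difference must exceed 1.608 (normal), 1.612 (pooled t, 128 df) or 1.619 (Welch, 47.8 df). The SAP states 1.62.
- Superiority power: (2.26 − 1.2)/0.2082 − 1.96 = 3.13, so 99.9%. This agrees with the protocol's 1000 successes in 1000 simulations but not with the SAP's 79%, which is a separate discrepancy.

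**Effect of pooling on the saline contrast.**
- Pooled variance, three-arm fit: (99 + 99 + 29*s*²)/227.
- Pooled variance, pairwise fit: (99 + 29*s*²)/128.
- Standard error used: pooled SD × 0.2082. Correct standard error: √(0.01 + *s*²/30).
- Width ratio = used/correct. One-sided error at a true difference of 1.2 = P(Z > 1.96 × ratio).

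| Saline SD (assumed) | Correct SE | Three-arm pooled SD | Ratio | Error | Pairwise pooled SD | Ratio | Error |
|---|---|---|---|---|---|---|---|
| 0.5 | 0.135 | 0.951 | 1.46 | 0.2% | 0.911 | 1.40 | 0.3% |
| 0.7 | 0.162 | 0.967 | 1.24 | 0.8% | 0.940 | 1.21 | 0.9% |
| 0.9 | 0.192 | 0.988 | 1.07 | 1.8% | 0.978 | 1.06 | 1.9% |
| 1.0 | 0.208 | 1.000 | 1.00 | 2.5% | 1.000 | 1.00 | 2.5% |
| 1.1 | 0.224 | 1.013 | 0.94 | 3.3% | 1.024 | 0.95 | 3.1% |
| 1.5 | 0.292 | 1.077 | 0.77 | 6.6% | 1.133 | 0.81 | 5.7% |

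Simulated three-arm regressions with baseline adjustment (10,000 per setting) gave errors of 0.2%, 2.4% and 6.4% at saline SDs 0.5, 1.0 and 1.5. With a separate variance per product the error was 2.4% to 2.7% for saline SDs from 0.5 to 2.0.

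**Effect on the decision at 2.26.** The distance to the margin is 1.06. The pooled three-arm half-width is 1.96 × pooled SD × 0.2082: 0.39 at *s* = 0.5 and 0.44 at *s* = 1.5. Power at *s* = 1.5 is P(Z < (1.06 − 0.44)/0.292), about 98% with the pooled variance, and P(Z < 1.06/0.292 − 1.96), about 95%, with separate variances.

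**Effect on non-inferiority, three-arm fit only.** The width ratio equals the pooled SD, so the errors are about 3.1%, 2.9% and 1.7% at *s* = 0.5, 0.7 and 1.5. If the two codes in the program are the two actives, the fit contains no saline side; simulated error was then 2.3% to 2.6% at every saline SD.

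**The case against.** A reader might infer more than the documents support, in three ways.

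**That the non-inferiority test is anti-conservative.** The printed program fits two treatments. If its codes follow the order of Table 1, it holds no saline side and the interval is unaffected. A three-arm fit is permitted by the prose but not shown. Even there, pairing works the other way: about 6 in 7 SoluPrep sides sit opposite a SoluPrep FF side, and the code ignores this. A left/right correlation ρ reduces the true variance of the contrast by a factor of about 1 − (6/7)ρ. At saline SD 0.5 the pooled variance is 0.904, so ρ = (1 − 0.904) × 7/6, about 0.11, cancels the whole effect. The correlation is not given either.

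**That the documents show unequal variances.** SAP 5.2 says "The baseline bacterial count requirements are in the range of 5.00 to 7.50" log10/cm², and a uniform spread over that window has SD 2.5/√12 = 0.72. That is a marginal baseline SD, under an assumed shape. It is not the residual SD of post-saline counts after baseline adjustment and cannot be set against 1.0. Protocol 8.1 simulates saline and active sides with the same SD of 1.0. It would equally be wrong to read a saline SD near 2.0 into the SAP's 79%, because the 1.62 threshold beside it fits an SD of 1.0 in both arms.

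**That the superiority claim is in danger.** The 6.6% applies when the true difference is exactly 1.2 and saline varies more than the actives. If saline varies less, the test is conservative.

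These objections stand. They leave untouched the fact that, in either fit, the saline interval depends on an equality the plan does not support.

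**Conclusion.** The point holds for the saline contrasts as a cheap gain in robustness; it is not a demonstrated error. The direction and size of any distortion are unknown because they depend on a saline SD that the documents do not give. A 10% difference in SD changes the saline width by only 6% to 7%; a saline SD of 1.5 against 1.0 would more than double the nominal error. Pooled-model power at 2.26 stays at about 98% or more for saline SDs up to 1.5, so the decision is unlikely to turn on this. For non-inferiority the effect is conditional on a three-arm fit and small: at most about 3.1% for saline SD 0.5 or more with independent sides, and conservative if saline varies more. All figures take the active SD as 1.0 and the sides as independent.

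**What to change.** Amend SAP 8.1, in prose and code, before unblinding:

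- State that the saline contrasts use a treatment-specific residual variance (REPEATED with GROUP=Treatment, keeping ddfm=kr, alongside whatever subject term is adopted), or heteroscedasticity-robust standard errors that also allow for two sides per subject.
- Estimate SoluPrep versus SoluPrep FF either from active sides only or from the same unequal-variance model, and say which.
- Define the treatment codes and show the code for the saline contrasts. Adding GROUP=Treatment to the program as printed may do no more than separate the two actives.

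The cost is a line or two of code, a few sentences, one or two extra variance parameters, and fewer degrees of freedom for the saline contrast. If the SDs are in fact equal, the required observed difference rises only from about 1.610 (226 df) to 1.619 (47.8 df), against a planning difference of 2.26.
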